15.29 Nursing guidelines

15.291 Pembrolizumab side effects vary greatly from those of traditional chemotherapy and can vary in severity from mild to life threatening. Instruct patients to report any side effects to the study team immediately. Side effects may be immediate or delayed up to months after discontinuation of therapy. Most side effects are reversible with prompt intervention of corticosteroids.

- 15.292 Diarrhea can be seen however is less common than that seen with anti-CTLA-4 agents. However it can be severe, leading to colonic perforation. Instruct patients to report ANY increase in the number of stools and/or change in baseline, blood in the stool, abdominal pain to the study team immediately.
- 15.293 Rash/pruritis/dermatitis is seen. Patients should report any rash to the study team. Treat per section 9.0 and monitor for effectiveness.
- 15.294 Monitor LFT's closely as elevations in these levels could indicate early onset autoimmune hepatitis. Patients should also be instructed to report any jaundice, or right upper quadrant pain to the study team immediately.
- 15.295 Pneumonitis can be seen and may be mild (only seen on imaging) to severe. Patients should be instructed to report any SOB, dyspnea, cough, chest pain, etc. to the study team immediately. Patients reporting these symptoms should have a pulse ox checked and consider immediate imaging per the treating MD.
- 15.296 Endocrinopathies (including hypopituitarism, hypothyroidism, hypophysitis, and adrenal insufficiency) are seen with this agent. Patients may present only with the vague sense of fatigue and "not feeling well". Additional symptoms may be that of nausea, sweating and decreased activity tolerance. Instruct patients to report these signs or symptoms immediately and obtain appropriate labs as ordered by MD.
- 15.197 Patients who are started on steroid therapy for any side effects of pembrolizimab toxicity should be instructed to take the steroids as ordered, and not to discontinue abruptly as symptoms may return and be severe. Patients may be on steroid therapy for weeks. Instruct patients to report any increase or change in side effects with any dosage decrease as patients may need a slower taper.
- 15.298 Fatigue is common and may or may not be associated with immune related side effects. Assess patient's fatigue level prior to each cycle of therapy and report any changes to the study team.
- 15.299a Patients should avoid receiving live vaccines within 30 days of study drug administration or per other study guidelines.
- 15.299b Patients who have undergone an allogenic bone marrow transplant, have an increased risk of severe complications including early GVHD, and venoocclusive disease, if they have previously been treated with pembrolizumab
- 15.299c Myocarditis has been reported and associated with pembrolizumab. Instruct patients to report chest pain, SOB, or dyspnea to study team immediately and/or seek emergency medical attention.
- 15.299d Autoimmune hematologic disorders including ITP and hemolytic anemia have been reported. Monitor blood counts closely and report any abnormalities to the study team.

15.299e Rare neurologic disorders including Guillain-Barre syndrome and myasthenia gravis have been reported. Instruct patients to report any neurologic symptoms including weakness, parasthesias or numbness, tingling to the study team immediately.

### 15.3 Dexamethasone for Oral Administration (DXM)

15.31 **Background:** Dexamethasone is an adrenal corticosteroid compound. Dexamethasone decreases inflammation by suppression of neutrophil migration, decreased production of inflammatory mediators, and reversal of increased capillary permeability; suppresses normal immune response. Dexamethasone's mechanism of antiemetic activity is unknown.

15.32 **Formulation:** Commercially available for oral administration as:  
Tablets [scored]: 0.5 mg, 0.75 mg, 1 mg, 1.5 mg, 2 mg, 4 mg, and 6 mg  
Solution, oral: 0.5 mg/mL (500 mL)  
Solution, oral concentrate: Dexamethasone Intensol: 1 mg/mL (30 mL)

15.33 **Preparation, storage, and stability:** Refer to package insert for complete preparation and dispensing instructions. Store oral tablets at room temperature between 20°C to 25°C (60°F to 77°F). Protect from moisture. Dispense in a well-closed, light-resistant container as defined in the USP/NF. Store oral liquid at room temperature, do not freeze. Do not use if solution contains a precipitate. Refer to commercial package for drug expiration date.

15.34 **Administration:** Refer to the treatment section for specific administration instructions. May be taken with meals to decrease GI upset.

15.35 **Pharmacokinetic information:**  
**Onset of action:** Prompt  
**Duration of metabolic effect:** 72 hours  
**Metabolism:** Hepatic  
**Half-life elimination:** Normal renal function: 1.8-3.5 hours; **Biological half-life:** 36-54 hours  
**Time to peak, serum:** Oral: 1-2 hours  
**Excretion:** Urine and feces

15.36 **Potential Drug Interactions:**  
**Cytochrome P450 Effect: Substrate of CYP3A4 (major); Induces CYP2A6 (weak), 2B6 (weak), 2C8 (weak), 2C9 (weak), 3A4 (strong)**  
**Increased Effect/Toxicity:** Aprepitant, azole antifungals, calcium channel blockers, cyclosporine, estrogens, and macrolides may increase the serum levels of corticosteroids. Corticosteroids may increase the hypokalemic effects of amphotericin B or potassium-wasting diuretics (loop or thiazide); monitor. Refer to the package insert for a listing of other drugs.  
**Decreased Effect:** Antacids and bile acid sequestrants may reduce the absorption of corticosteroids; may reduce the absorption of corticosteroids; separate administration by 2 hours. Aminoglutethimide, barbiturates, and CYP3A4 inducers may reduce the serum levels/effects of dexamethasone and dexamethasone may decrease the levels/effects of other CYP3A4 substrates. Serum concentrations of isoniazid may be decreased by

corticosteroids. Corticosteroids may lead to a reduction in warfarin effect. Corticosteroids may suppress the response to vaccinations.

**Ethanol/Nutrition/Herb Interactions:**

Ethanol: Avoid ethanol (may enhance gastric mucosal irritation).

Food: Dexamethasone interferes with calcium absorption. Limit caffeine.

Herb/Nutraceutical: Avoid cat's claw, Echinacea (have immunostimulant properties)

15.37 **Known potential adverse events:** Consult the package insert for the most current and complete information.

**Common known potential toxicities**, frequency not defined:

Fluid and electrolyte disturbances, congestive heart failure in susceptible persons, hypertension, euphoria, personality changes, insomnia, exacerbation of infection, exacerbation or symptoms of diabetes, psychosis, muscle weakness, osteoporosis, vertebral compression fractures, pancreatitis, esophagitis, peptic ulcer, dermatologic disturbances, convulsions, vertigo and headache, endocrine abnormalities, ophthalmic changes, and metabolic changes. Some patients have experienced itching and other allergic, anaphylactic or hypersensitivity reactions. Withdrawal from prolonged therapy may result in symptoms including fever, myalgia and arthralgia.

15.38 **Drug procurement:** Commercial supplies. Pharmacies or clinics shall obtain supplies from normal commercial supply chain or wholesaler.

15.39 **Nursing guidelines**

15.391 Monitor regularly for hypertension, CHF and other evidence of fluid retention.

15.392 Advise patient of possible mood or behavioral changes, i.e., depression, euphoria, insomnia, even psychosis. Instruct patient to report any suspected changes to healthcare team.

15.393 Assess for symptoms of gastric ulcer, heartburn, or gastritis. Suggest antacids. Instruct patient to report symptoms to healthcare team if unable to control.

15.394 Evaluate signs of infection, particularly local candidal infections and treat appropriately.

15.395 Monitor blood glucose frequently.

15.396 Instruct patient to report frequent, unrelenting headaches or visual changes to healthcare team.

15.397 Advise patient that easy bruising is a side effect.

## 16.0 Statistical Considerations and Methodology

### 16.1 Overview

This is a phase II study of a novel regimen of Pembrolizumab with ixazomib and dexamethasone for treatment of relapsed multiple myeloma patients requiring therapy. This study is designed to assess the overall response rate associated with therapy with pembrolizumab added to standard doses of ixazomib and dexamethasone in patients with relapsed multiple myeloma using a single stage phase II study design with an interim analysis.

16.11 Endpoint: The primary endpoint of the trial is the overall response rate. A success will be defined as a PR or better noted as the objective status on two consecutive evaluations. Response will be evaluated using all cycles. Throughout Section 16.0, response will be considered synonymous with “success”, unless specified otherwise.

16.12 Sample Size: The single-stage study design with an interim analysis to be used is fully described below. A minimum of 14 and a maximum of 37 evaluable patients will be accrued in the phase II study unless undue toxicity is encountered. We anticipate accruing an additional 4 patients to account for ineligibility, cancellation, major treatment violation, or other reasons for a maximum of 41 patients. All patients meeting the eligibility criteria who have signed consent and received at least one dose of treatment will be considered evaluable for response, with the exception of patients who are determined to be a major violation.

16.13 Accrual Rate and Study Duration: The anticipated accrual rate is 2-3 evaluable multiple myeloma patients per month. At this rate, it will likely take about 1.5 years to enroll the patients. The maximum total study duration is expected to be approximately 4.5 years, or until the last patient accrued has been observed for at least 3 years. The earliest date anticipated for presentation of results is at approximately 2 years, or when the last patient accrued has been observed for at least 6 months.

### 16.2 Statistical Design:

#### 16.21 Decision Rule:

A combination of ixazomib plus dexamethasone, an oral regimen, is effective for the treatment of relapsed multiple myeloma, with a response rate of 31% seen in a previous study that included 35 patients treated at the standard doses. An increase in the overall response rate with the addition of pembrolizumab to Ixazomib plus dexamethasone would be of interest.

The largest success proportion where the proposed treatment regimen would be considered ineffective in this population is 30%, and the smallest success proportion that would warrant subsequent studies with the proposed regimen in this patient population is 50%. The following one-stage design with an interim analysis is based on a Simon optimum design and requires 37 evaluable patients to test the null hypothesis that the true success proportion in this patient population is at most 30%.

16.211 Interim Analysis: Enter 14 evaluable patients into the study. If 4 or fewer successes are observed in the first 14 evaluable patients, we will consider this regimen ineffective in this patient population and terminate this study. Otherwise, if the number of successes is at least 5, we will continue accrual.

16.212 Final Decision Rule: Enter an additional 23 evaluable patients into the study. If 14 or fewer successes are observed in the first 37 evaluable patients, we will consider this regimen ineffective in this patient population. Otherwise, if the number of successes is at least 15, this will be considered evidence of promising activity and the treatment may be recommended for further testing in subsequent studies.

16.213 Over Accrual: If more than the target number of patients are accrued, the additional patients will not be used to evaluate the stopping rule or used in any decision making process. Analyses involving over accrued patients are discussed in Section 16.34.

16.214 NOTE: We will not suspend accrual at the interim analysis to allow the first 14 patients to become evaluable, unless undue toxicity is observed. Given the limited overall sample size and the inclusion of an adverse events stopping rule, we feel it is ethical to not halt accrual for the interim analysis. However, if accrual is extremely rapid, we may temporarily suspend accrual in order to obtain safety data on these patients before re-opening accrual to further patients

16.22 Power and Significance Level: Assuming that the number of successes is binomially distributed, the significance level is .095, i.e. there is a 9.5% chance of finding the drug to be effective when it truly is not. The probability of declaring that this regimen warrants further study (i.e. statistical power) and the probability of stopping after the interim analysis under various success proportions can be tabulated as a function of the true success proportion as shown in the following table.

If the true success proportion is...	0.30	0.35	0.40	0.45	0.50
Then the probability of declaring that the regimen warrants further study is...	0.095	0.253	0.474	0.694	0.853
And the probability of stopping after the interim analysis is ...	0.584	0.423	0.279	0.167	0.090

16.23 Other considerations: Adverse events, quality/duration of response, and patterns of treatment failure observed in this study, as well as scientific discoveries or changes in standard care will be taken into account in any decision to terminate the study

### 16.3 Analysis Plan

#### 16.31 Primary Outcome Analyses:

16.311 Definition: The primary endpoint in this trial is the overall response rate. A success is defined as a PR or better noted as the objective status on two consecutive evaluations. Response will be evaluated using all cycles. All patients meeting the eligibility criteria who have signed a consent form and have begun treatment will be evaluable for response, with the exception of patients determined to be a major violation.

16.312 Estimation: The proportion of successes will be estimated by the number of successes divided by the total number of evaluable patients. Confidence intervals for the true success proportion will be calculated according to the approach of Duffy and Santner.

#### 16.32 Secondary Outcome Analyses

16.321 The  $\geq$ VGPR response rate with pembrolizumab added to Ixazomib and dexamethasone will be estimated by the number of patients who achieve a VGPR, CR, or sCR at any time divided by the total number of evaluable patients. Exact binomial 95% confidence intervals for the true success rate will be calculated.

16.322 The complete response rate with pembrolizumab added to Ixazomib and dexamethasone will be estimated by the number of patients who achieve a CR or sCR at any time divided by the total number of evaluable patients. Exact binomial 95% confidence intervals for the true success rate will be calculated.

16.323 Survival time is defined as the time from date of first treatment to death due to any cause. The distribution of survival time will be estimated using the method of Kaplan-Meier.

16.324 Progression-free survival is defined as the time from date of first treatment to the earliest date of documentation of disease progression or death due to any cause. Patients who receive subsequent treatment for myeloma before disease progression will be censored on the date of their last disease assessment prior to initiation of the subsequent treatment. Transplant will not be considered subsequent treatment. The distribution of progression-free survival will be estimated using the method of Kaplan-Meier

16.325 Adverse Events: All eligible patients that have initiated treatment will be considered evaluable for assessing adverse event rate(s). The maximum grade for each type of adverse event will be recorded for each patient, and frequency tables will be reviewed to determine patterns. Additionally, the relationship of the adverse event(s) to the study treatment will be taken into consideration.

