**2.2 Secondary**

- 2.21 To determine the  $\geq$  very good partial response (VGPR) and complete response (CR) rate of pembrolizumab added to standard doses of ixazomib and dexamethasone in relapsed myeloma.
- 2.22 To determine the progression free survival and overall survival among patients with relapsed MM following treatment with the combination of pembrolizumab, ixazomib and dexamethasone.
- 2.23 To determine the toxicities associated with pembrolizumab added to standard doses of ixazomib and dexamethasone in patients with relapsed MM.

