**6.13 Prior to accepting the registration, registration/randomization application will verify the following:**

- IRB approval at the registering institution
- Patient eligibility
- Existence of a signed consent form
- Existence of a signed authorization for use and disclosure of protected health information

**6.14 Documentation of IRB approval must be on file in the Registration Office before an investigator may register any patients.**

In addition to submitting initial IRB approval documents, ongoing IRB approval documentation must be on file (no less than annually) at the Registration Office [REDACTED] If the necessary documentation is not submitted in advance

of attempting patient registration, the registration will not be accepted and the patient may not be enrolled in the protocol until the situation is resolved.

When the study has been permanently closed to patient enrollment, submission of annual IRB approvals to the Registration Office is no longer necessary.

- 6.15 At the time of registration, the following will be recorded:
  - Patient has/not given permission to store and use his/her sample(s) for future research of Multiple Myeloma at Mayo.
  - Patient has/not given permission to store and use his/her sample(s) for future research to learn, prevent, or treat other health problems.
  - Patient has/not given permission for MCCC to give his/her sample(s) to researchers at other institutions.
- 6.16 Treatment on this protocol must commence at a Mayo Clinic Institution, under the supervision of a hematologist.
- 6.17 Treatment cannot begin prior to registration and must begin ≤ 14 days after registration.
- 6.18 Pretreatment tests/procedures (see Section 4.0) must be completed within the guidelines specified on the test schedule.
- 6.19 All required baseline symptoms (see Section 10.61) must be documented and graded.
- 6.19a Blood draw kit is available on site, if applicable (see Section 14).

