#### **13.7 Ineligible**

A patient is deemed *ineligible* if after registration, it is determined that at the time of registration, the patient did not satisfy each and every eligibility criteria for study entry. The patient may continue treatment off-protocol at the discretion of the physician as long

as there are no safety concerns, and the patient was properly registered. The patient will go directly to the event-monitoring phase of the study (or off study, if applicable).

- If the patient received treatment, all data up until the point of confirmation of ineligibility must be submitted. Event monitoring will be required per Section 4.2 of the protocol.
- If the patient never received treatment, on-study material and the End of Active Treatment/Cancel Notification Form must be submitted. No further data submission is necessary.

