#### 16.52 Adverse Event Stopping Rules

The stopping rules specified below are based on the knowledge available at study development. We note that the Adverse Event Stopping Rule may be adjusted in the event of either (1) the study re-opening to accrual or (2) at any time during the conduct of the trial and in consideration of newly acquired information regarding the adverse event profile of the treatment(s) under investigation. The study team may choose to suspend accrual because of unexpected adverse event profiles that have not crossed the specified rule below.

Accrual will be temporarily suspended to this study if at any time we observe events considered at least possibly related to study treatment (i.e. an adverse event with attribute specified as “possible,” “probable,” or “definite”) that satisfy one of the following:

- if 2 or more patients in the first 6 treated patients experience a grade 4 or higher non-hematologic adverse event at least possibly related to treatment.
- if after the first 6 patients have been treated, 40% of all patients experience a grade 4 or higher non-hematologic adverse event at least possibly related to treatment.

We note that we will review Grade 4 and 5 adverse events deemed “unrelated” or “unlikely to be related”, to verify their attribution and to monitor the emergence of a previously unrecognized treatment-related adverse event.

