#### 16.6 Results Reporting on ClinicalTrials.gov:

At study activation, this study will have been registered within the [REDACTED] website. The Primary and Secondary Endpoints along with other required information for this study will be reported on [REDACTED]. For purposes of timing of the Results Reporting, the initial estimated completion date for the Primary Endpoint of this study is 3 years after the study opens to accrual. The definition of “Primary Endpoint Completion Date” (PECD) for this study is at the time all patients registered have been observed for 12 months.

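### Section 16.325 leaves treated patients later found ineligible out of the reported adverse-event rates, although toxicity is a named secondary goal and Section 13.7 requires their data.

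*Combined protocol and SAP*

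**What the plan says.** Toxicity is a stated secondary goal. Section 2.23 reads: "To determine the toxicities associated with pembrolizumab added to standard doses of ixazomib and dexamethasone in patients with relapsed MM". The matching analysis is in 16.325, which fixes the patient set: "All eligible patients that have initiated treatment will be considered evaluable for assessing adverse event rate(s". For those patients the maximum grade of each type of event is tabulated, with attribution taken into account.

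Section 13.7 defines ineligibility as something established after registration about the patient's status at registration, so it can come to light after dosing. It covers that case directly: "If the patient received treatment, all data up until the point of confirmation of ineligibility must be submitted". Event monitoring then follows under 4.2.

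Two neighbouring groups are handled differently. Cancels (13.9) leave before any study treatment, so they are not exposed. Major violations (13.8) are removed from the response set by 16.12 and 16.311, but 16.325 makes no such exception, so an eligible major violation stays in the adverse-event set.

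On reporting, 16.6 says: "The Primary and Secondary Endpoints along with other required information for this study will be reported on" the public registry.

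**The concern.** A toxicity rate describes what happened to people who took the drug. Whether a patient met every entry criterion is a separate matter. A patient dosed and then found ineligible was exposed, and any event in that patient is evidence about the regimen. Under 16.325 that evidence is collected and then left out of the summary that answers goal 2.23.

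The entry criteria cover organ function and blood counts (3.13), neuropathy (3.26), autoimmune disease (3.29b) and pneumonitis (3.29c). A patient who missed one of these could plausibly differ in adverse-event risk. That is an inference; the documents do not show it. Section 15.27 reports more serious side effects and deaths in myeloma when pembrolizumab was added to pomalidomide or lenalidomide with dexamethasone, so complete toxicity reporting has particular value for this combination. With at most 41 patients, a single omitted patient is visible in a rate.

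**Working it through.** **Which exposed patients fall outside 16.325**

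| Group | Exposed? | In the 16.325 set? |
|---|---|---|
| Eligible, treated | Yes | Yes |
| Eligible, treated, major violation (13.8) | Yes | Yes |
| Treated, later found ineligible (13.7) | Yes | No |
| Cancel (13.9) | No | No |

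Only the third group is affected. Section 16.34 brings over-accrued patients into the final estimates but does not bring in ineligible ones.

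**Inputs**

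- Evaluable target 37, allowance 4, maximum 37 + 4 = 41 (16.12).
- The allowance is shared among ineligibility, cancellation, major violation and other reasons (16.12).
- m = number of treated ineligible patients. The documents give no value, so m is an assumption with range 0 to 4. It is probably 0 or 1, because eligibility is checked at registration (6.13) and part of the allowance is for cancels, who are never treated.
- Eligible treated patients are taken as 37, assuming no eligible major violations and no over-accrual.
- Illustrative adverse-event count among the eligible: 8. This is hypothetical.

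**Formulas**

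- Share of treated patients left out = m/(37 + m).
- Rate under 16.325 = 8/37 = 21.6%.
- Rate in all treated patients runs from 8/(37 + m), if none of the m had the event, to (8 + m)/(37 + m), if all did.

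**Results**

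| m | Share left out | All-treated rate, lowest | All-treated rate, highest |
|---|---|---|---|
| 0 | 0% | 8/37 = 21.6% | 8/37 = 21.6% |
| 1 | 1/38 = 2.6% | 8/38 = 21.1% | 9/38 = 23.7% |
| 2 | 2/39 = 5.1% | 8/39 = 20.5% | 10/39 = 25.6% |
| 3 | 3/40 = 7.5% | 8/40 = 20.0% | 11/40 = 27.5% |
| 4 | 4/41 = 9.8% | 8/41 = 19.5% | 12/41 = 29.3% |

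The row m = 4 is a bound: it uses the whole allowance on treated ineligible patients, with no cancels. For an event not seen among the eligible, 0/37 = 0% could become 1/38 = 2.6% with one such patient, so the event would appear in the table only if that patient is counted.

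**Other denominators for m = 1.** If the other allowance places were filled by eligible patients, the share is 1/41 = 2.4%. If the trial stopped with 14 eligible patients treated, it is 1/15 = 6.7%; more may be treated by then, because 16.214 does not suspend accrual for the interim analysis.

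**The plan's own figures.** The plan states no adverse-event rate that could be reproduced. Its design figures are not in dispute. For the rule in 16.211 and 16.212 (continue with at least 5 of 14, success with at least 15 of 37), sum over x = 5 to 14 the binomial probability of x successes in 14 times the probability of at least 15 − x in the next 23. This gives 0.0954 at a true rate of 0.30 and 0.8526 at 0.50, against 0.095 and 0.853 in 16.22. Neither depends on the adverse-event set.

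**The case against.** The strongest reply is that the consequence is narrow. Registration has a gate: "Prior to accepting the registration, registration/randomization application will verify the following", and the list includes eligibility. Few if any patients should be dosed and then found ineligible. Case-report-form and expedited reporting (10.62, 10.41), the early safety analysis (16.4) and safety review by the monitoring board (16.51) carry no eligibility limit. What is left is a descriptive table on which no test, interval or decision depends. All of this stands and limits the weight of the point. It does not remove it: the wording excludes exposed patients from a named endpoint, and correcting it costs almost nothing.

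Some stronger readings are tempting, and the documents do not support them.

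- *That 16.325 contradicts 16.52.* The suspension rule counts without an eligibility limit: "if 2 or more patients in the first 6 treated patients experience a grade 4 or higher non-hematologic adverse event", and "if after the first 6 patients have been treated, 40% of all patients experience a grade 4 or higher non-hematologic adverse event". But one is a trigger for accrual and the other a final summary. They may use different sets, and patient protection does not run through 16.325.
- *That the reported rates are biased downward.* The omitted patients may have had more events or fewer, and the table above moves both ways.
- *That adverse-event data on these patients necessarily stop when ineligibility is confirmed.* Section 13.7 sets that cut-off for required data, but 10.81 has all adverse events recorded from consent through 30 days after treatment ceases, and 10.41 and 10.81 set serious-event windows without an eligibility limit. Because 13.7 also lets such a patient continue treatment off protocol, it is unclear which cut-off governs.
- *That the registry posting will be limited to the 16.325 set.* Section 16.6 does not say which patients the posted results use.
- *That the response analysis or the primary decision is faulty for the same reason.* Section 16.311 says: "All patients meeting the eligibility criteria who have signed a consent form and have begun treatment will be evaluable for response", with major violations excepted. That set is prespecified, agrees with 16.12 and matches the 37-patient rule, and nothing shows that exclusion is related to response. A response rate in all treated patients would be an optional addition; its absence is not an error.

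**Conclusion.** The point holds on the text: 16.325 excludes treated patients later found ineligible, 13.7 anticipates them and requires their data, and no other section supplies an all-treated safety set for reporting. The size is modest. At m = 1 the illustrative rate moves by between −0.5 and +2.1 percentage points; at m = 0 nothing changes. These figures rest on an assumed m, on 37 eligible treated patients and on a hypothetical 8 events. Confidence is high about the wording; whether any patient will be affected cannot be known from the documents. The defect is confined to a descriptive estimate for a secondary goal. It is a cheap improvement worth making before results are known.

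**What to change.** In 16.325, replace the restriction to eligible patients who started treatment with: all patients who received at least one dose of any study drug, regardless of eligibility.

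Add a footnote to the adverse-event tables giving the number of treated ineligible patients and the number of these whose adverse-event follow-up was shorter than for other patients. Before writing it, reconcile the cut-off in 13.7 (confirmation of ineligibility) with the recording window in 10.81 (consent through 30 days after cessation of treatment), so that it is clear how long events are recorded in these patients.

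The cost is a few words, one footnote and one clarification. Section 13.7 already requires these patients' data up to confirmation of ineligibility, so widening the set needs no new collection. Sample size, error rates, the 15-of-37 rule, 16.4 and 16.52 stay as they are. The downsides are that follow-up in the added patients may be truncated, which could under-count their events, and that reported rates may shift slightly in either direction. The footnote lets the reader judge both.
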